##### **3.1.2 Intervention arm - VPULSE®**

Once the operation is finished, a wound dressing is applied and a standard bandage is applied. It consists of one layer of soft synthetic bandage, stretching from proximal tibia to distal femur covered by a further layer of crepe bandage prior to or after tourniquet deflation, with 50% overlap of each layer. Once transferred to the ward for recovery, this standard bandage will be removed and VPULSE compression cryotherapy is applied to the patient's index knee. As with standard treatment arm, the VPULSE cuff is applied over the routine surgical wound dressing. The cryotherapy effect is achieved by circulating cold water using a pump rather than gravity-driven cryotherapy with the current Aircast Cryo/Cuff set up that is standard care. The VPULSE also achieves compression by intermittent dynamic compression; this is an approximate pressure of 50mmHG. Further info regarding VPULSE can be obtained from the Joint Operations website:

<https://www.jointoperations.co.uk/buy-online/vpulse/>

Apart from the difference in type of compression & cooling therapy, the protocol for both trial arms is identical. Used knee sleeves will be disposed of in line with local guidelines on disposal of clinical waste.

**Figures 1 & 2. CRYO/CUFF™ (left) and VPULSE® device (right)**

## 4. STUDY HYPOTHESIS

### 4.1 Primary objective

- To assess the efficacy of VPULSE® active compression & cooling device for reduction of post-operative pain after knee surgery compared with AIRCAST® KNEE CRYO/CUFF™ .

### 4.2 Secondary objective

- To assess the type of pain experienced by patients wearing either AIRCAST® KNEE CRYO/CUFF™ or VPULSE®.
- To assess the efficacy of VPULSE® for improvement of post-operative patient-reported outcome measures, including knee functionality, after knee surgery when compared with standard care AIRCAST® KNEE CRYO/CUFF™.

## 5. STUDY PROTOCOL

### 5.1 Study design, recruitment sites and timeline

This concerns a multi-centre, controlled prospective randomized study of CE-marked medical devices. The study will be carried out in the following NHS Trust:

- North Cumbria Integrated Care NHS Foundation Trust (both Cumberland Infirmary, Carlisle, and West Cumberland Hospital, Whitehaven. CI [name])

The study will take place in a hospital setting with support and oversight from the treating orthopaedic surgeon, nursing staff and research staff. Where appropriate, research delivery staff will be delegated to provide support with data collection and processing.

Table 2. Anticipated timeline

Month	Setup	Recruitment	Analysis	Finalise
Nov 2022	Submission for NRES/ HRA approval			
Dec 2022	NIHR portfolio adoption			
Jan 2023	NRES/HRA and Trust approval			
Feb 2023		Start recruitment		
Dec 2024		Finish recruitment		
Mar 2025			Follow-up complete; Analyse data.	
Jun 2025				manuscript & report writing

### 5.2 Participant identification and research setting

Participants will be recruited from orthopaedics clinics and all eligible patients will be invited to take part until the required numbers have been achieved. Identification will be by the orthopaedics clinical team, who are supporting the study. A screening form will be completed for potentially eligible patients to confirm that they indeed meet the trial criteria.

To summarise, the orthopaedic team will:

- Identify potentially eligible patients and ask verbal consent for them being approached about the study by a member of the R&D team
- Complete the incl/excl criteria part of the screening form (if a patient has given verbal consent to being approached by the research team then they can complete the screening form)

### **5.3 Consent and recruitment**

Those eligible will be approached and provided with an information pack and consent form, which will be signed to indicate that informed consent has been given. Patients will be given ample time to consider taking part, more than 24 hours if they wish. The study will be first mentioned at an orthopaedics out-patient clinic visit. The direct healthcare professional will first approach a patient about the study, and after verbal consent by the patient the healthcare professional themselves or a member of the research team can go through the informed consent process.

Patients are also allowed to consent to taking part when first approached as long as the study has been discussed with the patient and they have been given time to read the patient information leaflet and opportunity to ask any questions that they may have. Participants will receive no incentives and consent will be regarded as a process and not a one-off event. Participants are free to withdraw from the study at any time without the need to give any reasons for withdrawal. Their standard of care will not be affected by either declining to participate in the study or withdrawing during participation. Data collected up to the date of withdrawal will be retained for analysis.

Participants will be randomised to either the control group (Cryo/Cuff) or the intervention group (VPULSE) any time up until the day of surgery.

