#### **5.5.2 Secondary outcome measures**

All the outcome measures are summarised in Table 3.

Table 3. Overview of measurements

Weeks	-12 weeks to day of surgery	0 surgery	24hrs §	3 days ##	5 days ##	12 days #	6 weeks*	12 weeks
Application device post surgery		X	x					
VDS pain scale (at rest)	X		x	X	X	X	X	
VDS pain scale (walking, if capable to stand)	X		x	X	X	X	X	
McGill pain questionnaire	X		x	X	X	X	X	
Limb range of motion	X						X	
KOOS score	X						X	X
Patient satisfaction questionnaire re device use					X	X (if not returned yet at 5 days)		

\* Allowed to be up to 2 weeks early or late

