### 6.1.1 Randomisation

Following written consent patients will be allocated at random to the one of two treatment arms, the control AIRCAST® KNEE CRYO/CUFF™ or VPULSE® intervention group, using a non-restricted randomised sequence generated for the whole sample using a free ware randomisation programme, see <https://www.sealedenvelope.com/> . Each next randomisation allocation will be obtained from the sealedenvelope.com account for this ALASKA trial.

As the study involves different looking cooling devices, it is not possible to achieve blinding for the participants. However, statistical analysis is carried out blinded to group allocation, by persons who have not had contact with study participants.

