## 6.2 Eligibility criteria

### 6.2.1 Inclusion criteria

- Patient who is listed for:
  - Knee arthroplasty (replacement) surgery, either partial or total knee replacement (unilateral).
- Clinical indication, in the opinion of the treating surgeon, that compression & cooling therapy may be of benefit to the patient
- Adult patients aged > 18 years

- Mental capacity to give written informed consent

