## 8. STATISTICAL CONSIDERATION AND DATA ANALYSIS PLAN

### 8.1 Analysis of baseline characteristics

To determine the demographics and characteristics of the patients in the two arms the following data will be collated:

- Age (yrs)
- Gender
- Height (kg), weight (cm), BMI

Data concerning the actual knee replacement procedure will also be collected, including:

- Type of surgery
  - Including type of medical device used and which leg operated on
- Length of operation (min) and blood loss (ml) during operation
- Type of anaesthetic and analgesics prescribed post-surgery
- Hospital length of stay (days)
- Moment physiotherapy and early recovery initiated
- Type of standard bandaging applied if control patient.

Any differences in distribution will be established with Chi-squared test or Mann-Whitney U-test/t-test (depending on distribution of data) as indicated.

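### Randomisation is allowed at any time between consent and surgery, with no eligibility re-check described, although the arms do not differ until the ward

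*Protocol*

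**What the plan says.** Section 5.3 of the protocol allows allocation to either arm "any time up until the day of surgery". Section 6.1.1 gives written consent as the only trigger: "Following written consent patients will be allocated at random to the one of two treatment arms". Section 5.3 also permits consent at the first conversation: "Patients are also allowed to consent to taking part when first approached". No section gives an earliest date for allocation or a longest interval between allocation and surgery.

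At that stage the surgical inclusion criterion in section 6.2.1 is "Patient who is listed for" a partial or total unilateral replacement. On checking eligibility, section 5.2 says: "A screening form will be completed for potentially eligible patients to confirm that they indeed meet the trial criteria". No further check is described before allocation, surgery or fitting of the device.

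In theatre both arms receive the same wound dressing and standard bandage (sections 3.1.1 and 3.1.2). They separate only afterwards: "Once transferred to the ward for recovery, this standard bandage will be removed and VPULSE compression cryotherapy is applied". Section 6.1.1 says that participants cannot be blinded and that the analysts will be. It does not mention the theatre team.

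Section 6.1 specifies an intention-to-treat analysis and a 30% attrition allowance, explained by withdrawals and patients lost during follow-up. Section 8.1 records "Type of anaesthetic and analgesics prescribed post-surgery". Section 8.3 compares anaesthetic and analgesic type between the arms as a check on randomisation and refers back to these variables as regression covariates.

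**The concern.** Two things follow from allocating before the operation.

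First, allocation can come before the event that makes the primary outcome measurable. A patient who is randomised and then not operated on has no operation-site pain to report. Some of the section 6.2.2 exclusions can also change during a wait: anticoagulant treatment, a leg ulcer, a skin condition, entry into another knee study. Such patients belong to the randomised set but have no valid primary outcome. This loss after randomisation could be avoided by allocating later.

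Second, the arm can be known to those who choose the anaesthetic and write the first analgesic prescriptions. Both plausibly affect pain two days later. If they are chosen after the arm is known, a difference between the arms in these variables can no longer be read as chance, and adjusting for them may remove or create part of an effect. Section 8.3 treats them as if they came before allocation.

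**Working it through.** **1. Sequence of events, from the protocol's own sections**

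| Step | Where | Timing |
|---|---|---|
| Listed, screened | 5.2, 6.2.1 | Clinic |
| Consent | 5.3 | From first approach |
| Allocation | 5.3, 6.1.1 | Any time from consent to the day of surgery |
| Operation, same dressing and bandage in both arms | 3.1.1, 3.1.2 | Day of surgery |
| Allocated device first needed | 3.1.1, 3.1.2 | Ward, after theatre |

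The allocation is not used before the last row. Nothing done in theatre depends on it.

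**2. The plan's sample size**

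Inputs (section 6.1 and Table 4): difference 1.5 cm, SD 2 cm, two-sided alpha 0.05, power 80%, Mann-Whitney test, 30% attrition.

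- Effect size: 1.5 / 2 = 0.75.
- Mann-Whitney efficiency for normal data: 3/π = 0.955. With 31 per arm the effective size is 31 × 0.955 = 29.6.
- Non-centrality: 0.75 × √(29.6 / 2) = 2.89, on 2 × 29.6 − 2 = 57.2 degrees of freedom. Power is 81.0%.
- 31 per arm is the smallest size reaching 80%, so the stated 62 is reproduced.
- 62 / 0.70 = 88.6. The stated 88 agrees within rounding. It leaves 88 × 0.70 = 61.6 evaluable patients and 80.7% power.

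**3. Patients allocated without a valid primary outcome**

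The protocol gives no rate of cancelled or changed operations, or of patients becoming ineligible. Let f be that fraction; 5% to 15% is an assumption.

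- Number: 88 × 0.05 = 4.4 and 88 × 0.15 = 13.2, so about 4 to 13 patients.
- Allowance: 88 × 0.30 = 26.4. These patients would use 4.4 / 26.4 = 17% to 13.2 / 26.4 = 50% of it.

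If they fall within the 30%, planned power is unchanged. If they come on top, with the 30% applied to those who remain, the evaluable number is 88 × (1 − f) × 0.70, and the total needed to keep 62 is 62 / [0.70 × (1 − f)]:

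| f (assumed) | Evaluable of 88 | Power | Total needed to keep 62 |
|---|---|---|---|
| 0% | 61.6 | 80.7% | 89 |
| 5% | 58.5 | 78.6% | 94 |
| 10% | 55.4 | 76.3% | 99 |
| 15% | 52.4 | 73.8% | 105 |

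**4. Knowledge of the arm in theatre**

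No arithmetic applies. Section 6.1.1 blinds the analysts only, section 5.3 allows the arm to be known before theatre, and section 8.3 uses anaesthetic and analgesic type as comparability variables and covariates. The three fit together only if those choices cannot respond to the arm, and no section ensures that.

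**The case against.** The best defence is that section 5.3 already permits allocation on the day of surgery, so the protocol does not require early allocation. Allocating ahead may help staff to plan devices at two hospitals, given a limited supply under the grant in section 10.2. The screening form is not said to be completed only once, and a repeat check may sit in working procedures. The flowcharts in Appendices 2 and 3 are not shown and may settle the order of steps. How to analyse patients who are randomised but not operated on is commonly left to the analysis plan.

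Much of this stands. The lack of an analysis rule for such patients is not counted here. The planning advantage is real, though small. What remains is that the written rule on timing allows allocation at any earlier point, and an analysis plan cannot undo an allocation made too soon.

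Several stronger readings are tempting and are not supported:

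- **Allocation up to 12 weeks ahead.** A reader might take this from "12 weeks to day of surgery" in Table 3. That is the window for pre-operative measurements. The protocol sets no allocation window, so the interval may be shorter or longer.
- **Some patients will be allocated and never have an eligible operation.** Without a rate in the documents, only that some may.
- **The theatre team is told the arm.** No section says so; it is simply not prevented.
- **Later allocation would remove this bias.** Participants are unblinded, and ward staff who fit the device must know the arm, so analgesia prescribed on the ward stays exposed.

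**Conclusion.** The point holds as an inexpensive improvement to the design; it does not show that the trial is invalid. The protocol sets no limit on how early a patient may be randomised and describes no eligibility check close to surgery. It also leaves the arm open to the theatre team, although the device is first needed on the ward.

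The size of the loss cannot be fixed from the documents. The figure of about 4 to 13 of 88 rests entirely on an assumed 5% to 15%. Power is unchanged if the 30% absorbs these losses; if they are additional, it falls from 80.7% to between 78.6% and 73.8%. The argument about theatre-side choices needs no rate, but it concerns an open route for bias and not a demonstrated one. The conclusion holds whichever post-operative day is taken as primary (section 6.1 says day 5 where sections 5.5.1 and 8.2 say day 2), because either needs an operation.

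**What to change.** In sections 5.3 and 6.1.1, state that the allocation is obtained from the sealedenvelope.com account after the operation and before the standard bandage is removed on the ward. If that is impracticable, the earliest time should be the day of surgery, with the arm withheld from the theatre team.

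Add a short confirmation to the screening form, signed by the investigator or a delegate before the allocation is obtained: a unilateral primary partial or total replacement was performed, and no section 6.2.2 exclusion now applies. The check should be on the operation performed, since being listed for surgery cannot be re-confirmed afterwards. Exclusions that rest on the treating surgeon's opinion should be confirmed by the surgeon at the same time. Operative events may then decide who enters, which narrows the population slightly. Because the check comes before allocation, it cannot favour either arm.

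Consented patients who do not reach this point are logged as not randomised in the participant flowchart. The anaesthetic then becomes a true pre-allocation variable. Analgesia prescribed after allocation does not, and section 8.3 should not present it as a check on randomisation.

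The cost is a protocol amendment, one signature per patient, a web allocation on the day of surgery, and both devices available at each of the two hospitals. No change to the sample size is required.

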### **5.4 Follow-up**

Patients are in the study for a period of 12 weeks. Thereafter, the patient will be followed up as they would be in normal clinical practice. Study visits are aligned to hospital/clinic visits where possible. Baseline data can be collected on the day of surgery (prior the actual operation), and 12 day and 12 week post-surgery data can be collected when the patient attends for standard follow-up in the orthopaedics out-patient department. The data at 24 hrs, day 3, 5, and 12 falls outside these dates. For all outcome measures, data can be collected over the phone, via e-mail or by mail (whichever is preferred by the patient – mail is by use of freepost, to avoid patients incurring any costs). The researcher can also send reminders to the participant regarding the completion of certain outcome data at the aforementioned follow-up time points.

### **5.5 Outcome measures**

#### **5.5.1 Primary outcome measures**

To determine the level of operation-site related pain experienced at day 2 post-operation and to compare the average pain scores of patients in the control and intervention arm respectively, through administration of 10 cm visual descriptor scale (VDS) for pain.

The study is powered to detect the established minimal clinically important difference (MCID) of 1.5 cm on a 10 cm VDS pain.

#### **5.5.2 Secondary outcome measures**

All the outcome measures are summarised in Table 3.

Table 3. Overview of measurements

Weeks	-12 weeks to day of surgery	0 surgery	24hrs §	3 days ##	5 days ##	12 days #	6 weeks*	12 weeks
Application device post surgery		X	x					
VDS pain scale (at rest)	X		x	X	X	X	X	
VDS pain scale (walking, if capable to stand)	X		x	X	X	X	X	
McGill pain questionnaire	X		x	X	X	X	X	
Limb range of motion	X						X	
KOOS score	X						X	X
Patient satisfaction questionnaire re device use					X	X (if not returned yet at 5 days)		

\* Allowed to be up to 2 weeks early or late

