## RESEARCH PROTOCOL SUMMARY

TITLE:	A single-centre, two-arm, controlled, prospective randomized trial comparing AIRCAST® KNEE CRYO/CUFF™ passive compressive cryotherapy with VPULSE® active compressive cryotherapy after knee arthroplasty surgery
Short title:	ALASKA trial: Assessment of cooling Application poSt Knee Arthroplasty
IRAS number	322564
Device description	
VPULSE®
 
VPULSE® is designed to improve patient outcomes after injury and / or surgery through reduction of pain and swelling, with the aim to reduce the need for medication.
 
The VPULSE® system is used with anatomically designed pads, providing a continuous flow of cold and intermittent dynamic compression therapy.
 
Motorised cold therapy intended to reduce operative site discomfort and inflammation.

Study type	Medical device trial, involving CE-marked devices used for intended purpose.
Study design	Single-centre, two-arm, controlled, prospective randomized trial.
Patient population	
Adult participants who have unilateral knee replacement surgery (knee arthroplasty) and who meet the study inclusion criteria Participants must have the capacity to provide informed written consent and complete patient reported outcome measures.
 
The study has the following sample parameters: standard deviation of 2 cm per cohort, power beta of 80%, alpha p-value of 0.05. Sample size takes into account 30% attrition rate, effect size of 0.75 (mean difference of 1.5cm on 10cm visual analogue scale) based on previous ROBOT trial results.
 
Total of 88 patients:
 
 
- 44 Patients to receive AIRCAST® KNEE CRYO/CUFF™ (current standard care, control arm)
 
- 44 Patient to receive VPULSE® with knee-specific cuff (intervention arm)
 

Primary objective	To determine the level of operation-site related pain experienced at day 2 post-operation and to compare the average pain scores of patients in the AIRCAST® KNEE CRYO/CUFF™ and VPULSE® arm respectively, through administration of 10 cm visual descriptor scale (VDS) for 'at rest' pain.

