Secondary objectives	
Post-operative patient-reported outcome measures:
 
Prior to surgery and 24hrs, 3, 5, 12 days, and 6 weeks post-surgery
 
 
- Pain perception, using VDS pain (at rest and walking) and short form McGill pain questionnaire
 
 
Prior to surgery as baseline, and 6 and 12 weeks post-surgery, knee function and quality of life measurements
 
 
- Knee and Osteoarthritis Outcome Score (KOOS)
 
- Range of motion of the affected limb
 
 
Descriptive safety overview at 30 days and 12 weeks post-surgery:
 
 
- Readmitted to theatre and/or hospital
 
- Infection of wound site
 
- Diagnosed with pulmonary embolism or deep vein thrombosis.
 
 
Patient satisfaction survey at 5 days post-surgery

Sponsor	North Cumbria Integrated Care NHS Foundation Trust
Manufacturer & research grant provider	Joint Operations, supplier of VPULSE® active compression & cooling therapy device. Contact: [name], Business Development Manager, [contact] , email [contact] , www.jointoperations.co.uk , [name]
Chief Investigator	[name], consultant Orthopaedic Surgeon. North Cumbria Integrated Care NHS Foundation Trust. Phone numbers: [name], [contact]
Co-investigators	[name], consultant Orthopaedic Surgeon. North Cumbria Integrated Care NHS Foundation Trust, [contact]

	
[name], Orthopaedic Specialist Practitioner, North Cumbria Integrated Care NHS Foundation Trust, [contact]
 
[name] PhD, Science & Innovation Manager, [contact]; [contact] North Cumbria Integrated Care NHS Foundation Trust
 
[name], Orthopaedic Specialist Practitioner, North Cumbria University Hospitals NHS Trust, [contact]
 
[name], Advanced Nurse Practitioner, North Cumbria University Hospitals NHS Trust, [contact]

Organisation where research will take place	
North Cumbria Integrated Care NHS Foundation Trust Orthopaedics Department [name]

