## 6. SUBJECTS

### 6.1 Anticipated number of research subjects

The sample size calculation does take into account a 30% patient attrition rate (withdrawal and loss to follow-up), since this involves a study with multiple time points for data collection up to 12 weeks. From other similar studies we are aware that loss to follow-up is relatively high in this group of patients. Patients will be recruited from the adult (age 18+) population routinely seen by the evaluating clinical staff members. The primary outcome measure is based on knee/leg (ie wound site) pain experienced 5-days post-surgery based on the VDS pain scale 'at rest'. The hypothetical difference in pain perception is 1.5 on a 10 cm scale which equates to a significant 'minimally clinically important difference' for pain (Kelly 2001; Lee et al 2003; Tashjian et al 2009). The values and differences observed in the ROBOT trial will be used for reference.

The non-parametric two-sided Mann-Whitney u-test is applied because the data is ordinal; 80% power and 5% significance is also applied. A priori power calculations using GPower 3.1 software, result in the following sample size summarized in Table 3.

Analysis will be performed on an intention-to-treat basis, although the number of days that a participant has worn a bandage will be recorded.

Table 4, Sample size calculation

	Mean pain score at 5 days post-op	Standard Deviation
Arm A (hypothetical)	5.0	2
Arm B (hypothetical)	3.5	2
	Power beta of 80%, Alpha p-value of 0.05, Effect size 0.75  Sample size required without any drop-out: 62 Sample size with 30% attrition rate included: 88  Total of 88 patients: 
 
- 44 Patients to receive AIRCAST® KNEE CRYO/CUFF™ device (current standard care, control arm)
 
- 44 Patient to receive VPULSE® (intervention arm)
 
	

The CONSORT guidelines require a statement on the number of patients assessed for eligibility (Schulz, Altman & Moher 2010). The number of patients screened but who did not meet the inclusion criteria or who declined to participate will be recorded, as will any patients who are lost to follow-up (Appendix 3).

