## 8.2 Primary outcome statistics

To determine the level of operation-site related pain experienced at day 2 post-operation and to compare the average pain scores of patients in the control and intervention arm respectively, through administration of 10 cm visual descriptor scale (VDS) for pain.

The study is powered to detect the established minimal clinically important difference (MCID) of 1.5 cm on a 10 cm VDS pain.

The average difference between time points will be calculated per group, 2 days post-surgery being the primary endpoint. 24hrs, 3, 5, 12 days and 6 weeks post-surgery will also be analysed. To compare the groups, the Mann-Whitney U-test will be applied.

To avoid relying on one outcome measure related to pain, at 3, 5, 12 days, and 6 weeks post-surgery pain perception will also be measured using the short form McGill pain questionnaire. Again, to compare groups the Mann-Whitney U-test will be applied.

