### Visual Descriptor Pain score

How painful has your leg, the one has been operated on, been **in the last day when walking**:

Please put a vertical line on the numbered bar above. We kindly ask you consider the affected knee when you answer this question.

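### Walking pain is recorded only in patients who can stand, so this secondary comparison rests on a subset formed after randomisation and may be biased in either direction

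*Protocol*

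**What the plan says.** The Summary lists among the secondary objectives "Pain perception, using VDS pain (at rest and walking) and short form McGill pain questionnaire", with no condition attached. Table 3 in section 5.5.2 then schedules the walking item as "VDS pain scale (walking, if capable to stand" at baseline, 24 hours, days 3, 5 and 12, and 6 weeks. The rows for the at-rest VDS and the McGill questionnaire carry no such condition.

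The walking form in Appendix 1 asks "How painful has your leg, the one has been operated on, been", and completes the question with "been in the last day when walking". The text of the form gives no option for a patient who did not walk.

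On analysis, section 6.1 states "Analysis will be performed on an intention-to-treat basis", and section 8.2 says of the pain scores "To compare the groups, the Mann-Whitney U-test will be applied". The primary outcome is a different item: the Summary defines it "through administration of 10 cm visual descriptor scale (VDS) for 'at rest' pain", and section 6.1 also names the at-rest scale.

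**The concern.** Whether a patient can stand in the days after a knee replacement is settled after allocation and may depend on the pain that the device is meant to reduce. The protocol draws this link itself: the lay summary says that more pain may hold back mobilisation, and the introduction says that pain may impair early rehabilitation. A walking score taken only from those who can stand therefore compares two groups that randomisation did not form.

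The gap lies in data collection. The protocol provides for no record of inability, or of its reason, at each time point. Section 8.1 collects only when physiotherapy and early recovery began. Section 5.4 allows answers by phone, e-mail or post, so a blank walking score cannot be told from a skipped item. The condition also turns on standing while the form asks about walking, so a patient who stood but did not walk is asked a question with no valid answer.

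At stake is how a secondary result is read: a selected comparison would look like a full randomised one, and nobody could say which way it leaned.

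**Working it through.** **The plan's own figure.** Inputs from section 6.1, Table 4: means 5.0 and 3.5, SD 2, two-sided 5% significance, 80% power, Mann-Whitney test.

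- Effect size = (5.0 − 3.5)/2 = 0.75.
- The two-sample t-test needs 28.90 per arm. Dividing by the Mann-Whitney efficiency for normal data, 3/π, gives 30.26, so 31 per arm and 62 in total. This matches.
- With 30% attrition, 62/0.70 = 88.6, against the stated 88.

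This calculation is for at-rest pain. The figures are borrowed below as **assumed** walking scores, because the protocol gives none. It also gives no rate of inability to stand, so that is varied.

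**Inability driven by pain, same rule in both arms.** Scores are drawn as normal and clipped to 0–10, which makes the full difference about 1.47 cm. Patients above a cut-off go unscored. Power is for 31 per arm before removal, from 1,500 simulated trials per row (Monte Carlo error about ±0.02).

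| Assumed cut-off | Unscored, control / VPULSE | Difference seen (cm) | Shrinkage from 1.47 | P(control score > VPULSE score) | Power, left out | Power, ranked worst |
|---|---|---|---|---|---|---|
| none | 0 / 0 | 1.47 | – | 0.702 | about 0.81 | – |
| above 9 | 2.3% / 0.3% | 1.37 | 7% | 0.697 | 0.78 | 0.80 |
| above 8 | 6.7% / 1.2% | 1.26 | 14% | 0.690 | 0.73 | 0.80 |
| above 7 | 15.9% / 4.0% | 1.08 | 27% | 0.675 | 0.63 | 0.81 |
| above 6 | 30.8% / 10.6% | 0.86 | 41% | 0.658 | 0.48 | 0.80 |

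**Hand check without clipping.** The mean below a cut-off c is μ − σφ(z)/Φ(z), with z = (c − μ)/σ.

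- Cut-off 7: control 5 − 2(0.2420/0.8413) = 4.42; VPULSE 3.5 − 2(0.0863/0.9599) = 3.32; difference 1.10.
- Cut-off 6: control 3.98, VPULSE 3.09; difference 0.89.

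Both agree with the table apart from the effect of clipping.

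**Gradual rule.** With the chance of inability rising as 1/(1 + exp(−1.5(x − m))), midpoints m of 9, 8 and 7 give 1.36, 1.25 and 1.12 cm.

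**Other mechanisms, equally open on the document.**

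| Assumption | Unscored, control / VPULSE | Difference seen (cm) |
|---|---|---|
| Unrelated to pain, about 10% per arm | 10% / 10% | 1.47 (power 0.76) |
| Unrelated to pain, about 20% per arm | 20% / 20% | 1.47 (power 0.70) |
| VPULSE patients lose standing at lower pain (midpoints 9 v 5) | 4% / 26% | 2.05 |
| Control at random, VPULSE pain-related (midpoint 6) | 10% / 14% | 1.90 |
| No true effect, common cut-off 8 | 6.7% / 6.7% | 0.00 |
| VPULSE truly worse by 1.47, common cut-off 8 | 1.3% / 6.8% | 1.26 worse |

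**Worst-rank scoring is not safe in every case.** In the two rows unrelated to pain, ranking everyone unable as worst lowers power to 0.60 and 0.40. The reason must therefore be known before such a rule is applied.

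**The case against.** The strongest objection is that the direction is not established. A reader might infer that a real VPULSE benefit is bound to be understated. The documents do not support that: they give neither rates nor reasons for inability, and the second table shows that the bias can be absent or run the other way. This stands, and the point is put conditionally for that reason.

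Second, the larger losses need 16% or 31% of controls to be unable to stand. The form covers the whole last day, so any walking in it allows an answer, and the introduction says that stay rarely exceeds two days. This also stands. The milder cut-offs may be nearer the truth, and the effect would then be small.

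Third, a reader might infer that the primary result or the sample size is compromised. Neither is. The Summary and section 6.1 put the primary on the at-rest scale, and no power is claimed for walking pain. The at-rest VDS and the McGill items also still measure pain at these times in patients who cannot stand.

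Fourth, a reader might say that the analysis breaks the intention-to-treat statement. That is too strong: nothing in the protocol moves a patient out of the allocated arm. The accurate statement is that the comparison is conditional on a post-randomisation state.

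Fifth, the handling of unscored patients may sit in a statistical analysis plan that is not shown, so its absence here is no finding. But an analysis plan cannot recover inability or its reason if neither was collected, and the collection rule is fixed in this protocol.

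**Conclusion.** The point holds in conditional form, for a secondary outcome. As Table 3 and the walking form stand, walking pain is compared in patients selected after randomisation, by a state that pain can cause, and those left out are not documented.

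If inability is pain-driven alike in both arms and VPULSE works, the difference seen shrinks by about 7% to 41% over the assumed cut-offs; a true harm shrinks in the same way. If inability is unrelated to pain, there is no bias, only lost precision. If it differs by arm, the benefit may be overstated (1.90 or 2.05 cm against 1.47 in the two cases tried) or harm hidden. All these sizes rest on borrowed at-rest figures and assumed rates. They illustrate the possible bias and do not predict it.

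**What to change.** - **Table 3 and the walking form:** replace the standing condition with a tick-box at each time point, for example: *did not walk in the last day: because of knee/leg pain / other reason*. This also removes the mismatch between standing and walking.
- **Reporting:** give the proportions who did not walk, by arm, reason and time point.
- **Section 8.2:** keep the Mann-Whitney test among those who walked and state that it is conditional on walking. Add a pre-specified sensitivity analysis that ranks pain-related inability as the worst outcome and treats other reasons as missing.

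The cost is one form item and a few sentences. The downside is that unblinded patients attribute the reason themselves, which can itself introduce bias, so the worst-rank result should be read as a sensitivity analysis only.
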